# 4.3 Appropriateness of Measurements

STT measurements are an easy and effective method to measure NMC (Rutland and Cole 1981), whereby a 1-2 mm particle of saccharin is placed on the inferior nasal turbinate, 1 cm from the anterior end. The study participant will remain sitting for the duration of the test without speaking or engaging in any other activities that would disrupt the evaluation. The study participant will report when saccharin can be tasted and the time elapsed will be recorded and used as a measure of NMC (Rutland and Cole 1981). NMC strongly correlates with ciliary motility and function such that the greater the observed transit time, the further that ciliary motility and function is decreased (D. Passàli, Bellussi, & De Seta, 1984; D. Passàli & Bianchini, 1985; D. Passàli, Ferri, Becchini, Passàli, & Bellussi, 1999). The STT test has been

#### **Confidentiality Statement**

Data and information contained in this document are considered to constitute trade secrets and confidential commercial information, and the legal protections provided to such trade secrets and confidential information are hereby claimed under the provisions of applicable law. No part of this document may be publicly disclosed without the written consent of Philip Morris Products S.A.

Philip Morris Products SA	Clinical Study Protocol	Confidential
P1-CMS-01-US	Final 2.0 Amendment 1.0, 22-May-2017	Page 45 of 106

CSP

Related to PMI\_RD\_WKI\_000759

considered a "gold-standard" procedure for assessing NMC function as it permits large-scale assessment outside of specialized respiratory centres.

All laboratory measures utilized for this study are validated and are appropriate for the study assessments.

Since the test for nicotine concentration is highly sensitive, all study personnel who will be collecting blood must be non-smokers.

# 4.4 Study Duration

The planned maximum study duration for a single study participant from Screening through completion of study will be 33 days.

The estimated maximum study duration for the whole Study from screening through completion will be 35 days.

# **5** STUDY POPULATION

This study will enroll 14 study participants: 7 cigarette smokers and 7 never smokers.

The subjects will be divided in two groups:

Group 1 - 7 cigarette smokers

Group 2 - 7 never smokers

## **5.1** Selection of Study Population

An overview of the timing for assessment of each inclusion and exclusion criteria can be found in the Appendix B – Inclusion and Exclusion Criteria Assessment

## 5.1.1 Inclusion Criteria

Subjects who meet all the following inclusion criteria can be enrolled into the study:

- 1. Informed of the nature of the study and have agreed to and are able to read, review, and sign the informed consent form (ICF) prior to Screening. The subject must be willing to comply with the study procedures described in the informed consent. The informed consent document will be written in English, therefore the volunteer must have the ability to read and communicate in English.
- 2. Male subject aged  $\geq 25$  to  $\leq 45$  years old.
- 3. BMI between  $18.0 \text{ kg/m}^2$  to  $32.0 \text{ kg/m}^2$ , inclusive.
- 4. Judged by the Principal Investigator or designee to be in good health as documented by the medical history, physical examination, vital sign assessments, clinical laboratory assessments, and by general observations.
- 5. Belong to one of the following two groups:
  - a. Non-menthol cigarette smoker (meets all of the following criteria at Visit 1 and at Visit 2):

#### **Confidentiality Statement**

Data and information contained in this document are considered to constitute trade secrets and confidential commercial information, and the legal protections provided to such trade secrets and confidential information are hereby claimed under the provisions of applicable law. No part of this document may be publicly disclosed without the written consent of Philip Morris Products S.A.

Final 2.0 Amendment 1.0, 22-May-2017

Related to PMI RD WKI 000759

i. A positive urine cotinine test ( $\geq 200$ ng/mL).

- ii. Smoked at least 20 cigarettes per day for at least the past 5 years.
- iii. eCO levels >10 parts per million (ppm).
- iv. No plans to quit smoking in the next 3 months.
- b. Never smoker (meets all of the following criteria at Visit 1 and at Visit 2):
  - i. Subject who has smoked less than 100 cigarettes throughout their lifetime and no cigarettes in the past 3 years.
  - ii. A negative urine cotinine test (<200 ng/mL).
  - iii. eCO levels  $\leq$  5 ppm.
- 6. Completed the Screening process within 30 days prior to Visit 2.
- 7. Availability for the entire study period and willingness to comply with study procedures, including smoking interruptions, as evidenced by a signed ICF and at Visit 2.

## 5.1.2 Exclusion Criteria

Subjects who meet any of the following exclusion criteria must not be enrolled into the study:

- 1. As per the Principal Investigator or designee's judgment, the subject cannot participate in the study for any reason (e.g., medical, psychiatric, and/or social reason).
- 2. Subject is legally incompetent, or physically or mentally incapable of giving consent (e.g., emergency situation, under guardianship, prisoners, or subjects who are involuntarily incarcerated).
- 3. Presence of confounding allergies including allergic rhinitis and non-allergic rhinitis during the course of the study based on medical history and SPT.
- 4. Clinical significant abnormality on their nasal and throat exam, at the discretion of the Principal Investigator or designee at Visit 1 and/or at Visit 2.

## **Confidentiality Statement**

Data and information contained in this document are considered to constitute trade secrets and confidential commercial information, and the legal protections provided to such trade secrets and confidential information are hereby claimed under the provisions of applicable law. No part of this document may be publicly disclosed without the written consent of Philip Morris Products S.A.

Confidential

P1-CMS-01-US

Final 2.0 Amendment 1.0, 22-May-2017

Page 48 of 106

Related to PMI\_RD\_WKI\_000759

5. Cigarette smoker who smoke/use any tobacco or nicotine products, such as cigars, pipe, menthol cigarettes or electronic cigarettes in the previous 3 months, as self-reported at Visit 1 or Visit 2.

- 6. Never smoker who smoke/use any tobacco or nicotine products, such as cigars, pipe, menthol cigarettes or electronic cigarettes in the previous 3 years, as self-reported at Visit 1 or Visit 2.
- 7. Cigarette smokers who state they will be unable to abstain from smoking for up to 24 hours.
- 8. Inability to taste sweet within 60 minutes in the STT test.
- 9. Subjects who routinely use or who have used in the previous 4 weeks nasal sprays, inhalers or other nasal products, such as nasal irrigation (for example, Neti Pot) prior to Visit 1 and/or Visit 2.
- 10. Subjects who have taken any of the following medication without the indicated minimum washout period:

Prohibited Medication	Restriction period (with Principal Investigator or designee discretion)
Short-acting antihistamines including intranasal antihistamines	3 days before Visit 1 until Visit 2
Long-acting antihistamines (i.e. Loratadine, Desloratadine)	7 days before Visit 1 until Visit 2
Over-the-counter cough and cold preparations or sleep aids containing antihistamines	3 days before Visit 1 until Visit 2
Leukotriene inhibitors	14 days before Visit 1 until Visit 2
Oral or intra-articular steroid	30 days before Visit 1 until Visit 2
Intranasal and inhaled corticosteroids	14 days before Visit 1 until Visit 2
Use of monoamine oxidase inhibitors	14 days before Visit 1 until Visit 2
Decongestants	48 hours before Visit 1 until Visit 2

#### Table 1 - Prohibited medication.

#### **Confidentiality Statement**

Data and information contained in this document are considered to constitute trade secrets and confidential commercial information, and the legal protections provided to such trade secrets and confidential information are hereby claimed under the provisions of applicable law. No part of this document may be publicly disclosed without the written consent of Philip Morris Products S.A.

Confidential

P1-CMS-01-US

Final 2.0 Amendment 1.0, 22-May-2017

Page 49 of 106

Related to PMI\_RD\_WKI\_000759

Cromolyn products	14 days before Visit 1 until
	Visit 2
Beta-adrenergic blockers (i.e. Acebutolol, Atenolol, etc.)	14 days before Visit 1 until
	Visit 2
Antishalinargies	7 days before Visit 1 until Visit
Anticholinergics	2
	On the day of Visit 1 until
Herbal or natural product remedies for allergy symptoms	Visit 2
	6 hours prior to spirometry
Short-Acting Beta Agonists	(except as per protocol before
	spirometry)
	3 days before Visit 1 until Visit
Long-Acting Beta Agonists	2
Phosphodiesterase 5 inhibitors (i.e. Sildenafil, Vardenafil,	7 days before Visit 1 until Visit
Tadalafil)	2
	3 days before Visit 1 until Visit
Amiloride	2
	7 days before Visit 1 until Visit
Macrolide antibiotics	2
	3 days before Visit 1 until Visit
Guaifenesin	$\frac{1}{2}$
	14 days before Visit 1 until
Mucolytic agents	Visit 2
	14 days before Visit 1 until
Topical menthol products	Visit 2
	4 weeks before Visit 1 until
Topical nasal medication	
	Visit 2
Topical ocular medication	4 weeks before Visit 1 until
*	Visit 2
Any other medication at the Principal Investigator or designee's	As per Principal Investigator
discretion that might interfere with the endpoints or procedures.	or designee.

11. Subjects with evidence of COPD, Global Initiative for Chronic Obstructive Lung Disease GOLD stage I or greater, and a forced expiratory volume 1 / the forced vital capacity ratio (FEV1/FVC ratio) <0.7.

#### **Confidentiality Statement**

Data and information contained in this document are considered to constitute trade secrets and confidential commercial information, and the legal protections provided to such trade secrets and confidential information are hereby claimed under the provisions of applicable law. No part of this document may be publicly disclosed without the written consent of Philip Morris Products S.A.

Final 2.0 Amendment 1.0, 22-May-2017

Page 50 of 106

Related to PMI\_RD\_WKI\_000759 CSP

- 12. Any condition the Principal Investigator or designee has cause to believe would interfere with the procedures for upper or lower airway function. This could include, but is not limited to, nasal/septum deviations, or nasal polyps or nasal allergies which will be identified by the Principal Investigator or designee.
- 13. Upper or lower respiratory diseases in the 4 weeks prior to Visit 2.
- 14. History of nasal or sinus surgery in the 5 years prior to Visit 2.
- 15. As per the Principal Investigator or designee's judgment, the subject has medical conditions which require or will require in the course of the study, a medical intervention (e.g., start of treatment, surgery, hospitalization) which may interfere with the study participation and/or study results.
- 16. The subject has a positive alcohol test and/or a history of alcohol abuse that could interfere with the subject's participation in study at Visit 1 or Visit 2.
- 17. Positive urine drug screen at Visit 1 or Visit 2.
- 18. The subject has positive serology test for human immunodeficiency virus (HIV)1/2, Hepatitis B or Hepatitis C.
- 19. Subject has donated or been in receipt of whole blood or blood products within 3 months prior to Visit 1.
- 20. Subject is a current or former employee of the tobacco industry or of their first-degree relatives (spouse, legal partner, parent, sibling, and child).
- 21. Subject is an employee of the investigational site or any other parties involved in the study or of their first-degree relatives (spouse, legal partner, parent, sibling, and child).
- 22. Subject has been in receipt of last dose from another clinical study within 3 months prior to Visit 1.
- 23. Subject has been previously screened in this study.

# **5.2** Discontinuation of Study participants from the Study

Discontinued study participants will include both study participants who withdraw from the study (study participant's decision) or study participants who are removed from the study by the Principal Investigator. A study participant can only be discontinued from the study after enrollment.

Study participants will be informed that they are free to withdraw from the study at any time. Study participants should be questioned for the reason of premature withdrawal from the study, although they are not obliged to disclose it. This needs to be fully documented in the source document and case report form (CRF).

If the study participant withdraws his consent for the study, the Principal Investigator or designee needs to document if:

- The study participants agrees that the data can be used until the time of withdrawal.
- The study participant agrees to have his samples collected until the time of withdrawal to be analyzed.

This information needs to be fully documented in the source document and CRF.

When a study participant is discontinued from the study, he will be asked to perform the examination procedure planned in Section 9.4 as soon as possible after the time of discontinuation, unless the study participant is not willing to perform any additional assessment.

Study participants discontinued from the study cannot re-enter the study.

Study participants must be discontinued from the study for any of the following reasons:

- Withdrawal of informed consent.
- Any AE or condition (including clinically relevant changes in a laboratory parameter) which at the discretion of the Principal Investigator no longer justifies the study participant's participation in this study.
- The Sponsor or the Principal Investigator terminates the study. If the Sponsor or the Principal Investigator decides to prematurely terminate the study, the study participant

## **Confidentiality Statement**

Data and information contained in this document are considered to constitute trade secrets and confidential commercial information, and the legal protections provided to such trade secrets and confidential information are hereby claimed under the provisions of applicable law. No part of this document may be publicly disclosed without the written consent of Philip Morris Products S.A.

Philip Morris Products SA

Clinical Study Protocol

Confidential

P1-CMS-01-US

Final 2.0 Amendment 1.0, 22-May-2017

Page 52 of 106

Related to PMI\_RD\_WKI\_000759

will be promptly informed. The Principal Investigator should report the fact and the reason of termination in writing to the IRB.

• Discontinuation is considered to be in the best interest for the study participant himself or for other study participants participating to the study.

Study participants may be discontinued from the study for any of the following reasons:

• Non-compliance to the study procedures based on the judgment of the Principal Investigator.

Study participants discontinued prematurely after enrollment will not be replaced and will not be allowed to re-enter the study. All study participant discontinuations must be documented properly in the source document and in the CRF.

# 5.3 Lost to Follow-up

Not applicable.

# 5.4 Violation of Selection Criteria

Study participants who are eligible at Screening (Visit 1), but who do not meet the entry criteria at Visit 2, will be considered as a screen failure until enrollment is completed.

If a violation of selection criteria after enrollment is detected, the study participant may be discontinued from the study at the discretion of the Principal Investigator or designee. If study participants are not yet enrolled, they can be replaced. If study participants are enrolled, and the Principal Investigator decides that they should be discontinued from the study, they will not be replaced.

# **6** INVESTIGATIONAL PRODUCTS

Not applicable.

## 6.1 Restrictions

## 6.1.1 Smoking Restrictions

Study participants will be allowed to use their own brand of cigarettes.

After enrollment, and between Visit 2 and Visit 3, the smokers group (group 1) will abstain from smoking for a period of 8 hours. At Visit 3, after the 8 hour smoking abstinence period, the smokers will smoke 1 single cigarette.

The subjects enrolled in the never smokers group (group 2) will not be allowed to smoke during the entire study duration.

For both groups 1 and 2, there will be no smoking restriction after the discharge at Visit 3 and during the 1 day follow-up period.

## 6.1.2 Dietary Restrictions

Study participants are not allowed to bring their own food or beverages to the investigational site. No food or drinks will be allowed during the conduct of the STT test except for the required glass of water (approximately 240 mL) before conducting the STT tests. Meals will be served according to the schedules provided in Section 9. Additional light snacks, fruits, and raw vegetables may be distributed to the study participants (except during STT tests). Consumption of water is allowed as desired (except during STT tests as described above).

# 6.2 Concomitant Medication

Prohibited medication is described under exclusion criteria 10 (Table 1, depicted below).

Table 1 - Prohibited medication.

Prohibited Medication	Restriction period (with Principal Investigator or designee discretion)
Short-acting antihistamines including intranasal antihistamines	3 days before Visit 1 until Visit 2
Long-acting antihistamines (i.e. Loratadine, Desloratadine)	7 days before Visit 1 until Visit 2
Over-the-counter cough and cold preparations or sleep aids containing antihistamines	3 days before Visit 1 until Visit 2
Leukotriene inhibitors	14 days before Visit 1 until Visit 2
Oral or intra-articular steroid	30 days before Visit 1 until Visit 2
Intranasal and inhaled corticosteroids	14 days before Visit 1 until Visit 2
Use of monoamine oxidase inhibitors	14 days before Visit 1 until Visit 2
Decongestants	48 hours before Visit until Visit 2
Cromolyn products	14 days before Visit 1 until Visit 2
Beta-adrenergic blockers (i.e. Acebutolol, Atenolol, etc.)	14 days before Visit until Visit 2
Anticholinergics	7 days before Visit 1 until Visit 2
Herbal or natural product remedies for allergy symptoms	On the day of Visit 1 until Visit 2
Short-Acting Beta Agonists	6 hours prior to spirometry (except as per protocol before spirometry)

#### **Confidentiality Statement**

Confidential

P1-CMS-01-US

Final 2.0 Amendment 1.0, 22-May-2017

Page 55 of 106

Related to PMI\_RD\_WKI\_000759 CSP

Long-Acting Beta Agonists	3 days before Visit 1 until Visit 2
Phosphodiesterase 5 inhibitors (i.e. Sildenafil, Vardenafil, Tadalafil)	7 days before Visit 1 until Visit 2
Amiloride	3 days before Visit 1 until Visit 2
Macrolide antibiotics	7 days before Visit 1 until Visit 2
Guaifenesin	3 days before Visit 1 until Visit 2
Mucolytic agents	14 days before Visit 1 until Visit 2
Topical menthol products	14 days before Visit 1 until Visit 2
Topical nasal medication	4 weeks before Visit 1 until Visit 2
Topical ocular medication	4 weeks before Visit 1 until Visit 2
Any other medication at the Principal Investigator or designee's discretion that might interfere with the endpoints or procedures.	As per Principal Investigator or designee.

Note: drugs included in the list above cannot be used during the study, from enrollment until discharge on Visit 3. In case the subjects use any of the above mentioned drugs, that use will be recorded in the eCRF and the Principal Investigator will decide on the subject permanence on the study.

# **7** STUDY PROCEDURES

Personnel performing study assessments must have the appropriate training and full documentation. An overview of all study assessments is shown in the Schedule of Events (Appendix A). In this section, only the expected/planned timepoints for the various assessments are described. As not all study participants can undergo a procedure at the same time, adequate time windows are given for each study procedure and each timepoint (Section 9). Site personnel will adhere to the internal SOPs for all activities. Appropriate medical advice will be provided to the study participant in case of any medical findings requiring health care.

## 7.1 Informed Consent

Prior any study assessments is performed, the subject will be asked to provide his written consent to participate to the study (ICF/subject information sheet for study participation) (Section 1.3). All assessments must start after the time of ICF signature by the subject for study participation.

# **7.2** Clinical Assessments

Any clinically relevant medical condition detected at Visit 1 has to be documented as a concomitant disease. This also applies to clinically relevant findings in laboratory values and vital signs detected at Visit 1. Any untoward medical occurrence in a study participant detected during the study which was not present at Visit 1 must be documented as an AE. Worsening of a pre-existing condition from Visit 1 onwards will also be documented as an AE. If a clinically relevant finding is detected at Visit 1, the Principal Investigator or designee will need to check if the inclusion criterion No. 4 is still fulfilled.

The results of the clinical assessments described in this section will be recorded in the CRF.

Any abnormalities or deviations outside the normal ranges for any clinical testing (laboratory tests, etc.) can be repeated at the discretion of the Principal Investigator or designee and judged to be not clinically significant for study participation. Any abnormalities or deviations outside

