## 7.2.4 Medical History, Concomitant Disease, Previous and Ongoing Medications

Relevant medical history will be documented at the Screening Visit. Medical history is defined as any condition that started and ended prior to the Screening Visit. Any concomitant disease will be documented at the Screening Visit. A concomitant disease is defined as any condition that started before and was going on at the time of ICF signature.

All medication taken 30 days prior to Visit 1 and all concomitant medication taken during the study will be documented in the source documentation and recorded in the CRF. Medication which was started prior to Visit 1 and which is still being taken by the study participant during the study as well as medication that is initiated after Visit 1 will be considered as a concomitant

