# 8.2.2 Period of Collection

Starting from the time when consent was obtained, the PI or designee will record all adverse events observed, queried, or spontaneously reported by the study participants. An adverse event query will be performed as scheduled as per Principal Investigator or designee's direction at the screening visit and throughout the confinement period and prior to being released from

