# **11.2** Data Handling

All study data will be managed by the Data Management Team at the CRO. The Data Management Team at the CRO will prepare a Data Management Plan (DMP). This document will describe, in details, the Data Management-related procedures and processes. The overall procedures for quality assurance of clinical study data are described in the SOPs of the CRO Data Management Team and/or Data Management Plan (DMP).

Data of all study participants enrolled, including screening failures and AE during the study (from the time of Informed Consent to the end of the safety follow-up period) will be captured in the source documents. All enrolled subjects will be entered in the study database (eCRF).

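### Protocol 7.2 files clinically relevant Visit 1 findings as concomitant disease, while 7.2.4 and 8.2.2 draw the line at consent, so a new reaction to a Visit 1 procedure could be left out of the AE data

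*Protocol*

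**What the plan says.** Protocol 7.2 (Clinical Assessments) classifies findings by the visit at which they are seen. "Any clinically relevant medical condition detected at Visit 1 has to be documented as a concomitant disease". The rule is then widened: "This also applies to clinically relevant findings in laboratory values and vital signs detected at Visit 1". For adverse events it says: "Any untoward medical occurrence in a study participant detected during the study which was not present at Visit 1 must be documented as an AE". A further sentence also counts as an AE any deterioration, from that visit on, of a condition already there.

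Other parts of the protocol classify by onset relative to consent, or leave room for an AE at screening:

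- 7.2.4: "A concomitant disease is defined as any condition that started before and was going on at the time of ICF signature".
- 8.2.2: "Starting from the time when consent was obtained, the PI or designee will record all adverse events observed, queried, or spontaneously reported". The same section places an AE query at the screening visit.
- Appendix A marks AE recording at Visit 1.
- 8.5.1 treats screening laboratory abnormalities of CTCAE grade 2 or higher, or of grade 1 if clinically significant, as usually concomitant disease. It lets the investigator assess them as AEs case by case.
- 7.1 requires the consent form to be signed before any assessment starts.

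The SAP (5.5.4.2) reports AEs for the safety population, which is all enrolled subjects, in Tables A 11 and A 12. It sets no rule of its own for when an AE begins.

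**The concern.** The two boundaries differ for anything that starts between consent and the end of Visit 1, which is when the screening procedures are done. Appendix A schedules post-bronchodilator spirometry, which includes four inhaled doses, and the skin prick test at Visit 1 and at no other visit. No later visit can supply safety information on them.

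A reaction filed as concomitant disease would not get the relatedness judgement of 8.2.4. That is the study's only causality assessment, because there is no investigational product. The reaction would not be counted in Tables A 11 and A 12. It would also become the pre-existing condition against which later worsening is judged. Safety monitoring is a stated secondary objective.

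**Working it through.** The plan gives no figure to reproduce. The check sets the rules side by side for each kind of event.

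| Event | Under 7.2 | Under 7.2.4, 8.1.1 and 8.2.2 |
|---|---|---|
| Began before consent, still present at Visit 1 | Concomitant disease | Concomitant disease |
| New, clinically relevant, began after consent, seen at Visit 1 | Concomitant disease | AE |
| New, began after Visit 1 | AE | AE |
| Pre-existing condition that worsens from Visit 1 onwards | AE | AE |
| Clinically relevant laboratory abnormality in the Visit 1 sample, onset unknown | Concomitant disease | Not settled by onset; 8.5.1 says usually concomitant disease, possibly AE |

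The rules disagree in the second row and, for laboratory results, in the fifth.

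**Does the second row occur?** By 7.1 every Visit 1 procedure comes after consent, so any reaction to one begins after consent. If it is clinically relevant and noticed before the participant leaves, it falls in this row. The worsening sentence in 7.2 does not rescue it, since that sentence needs a condition that already existed.

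**Does a later step correct it?** The SAP has no start window or emergence rule for AEs, so the AE tables depend on how the site classified the event.

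**Scale.** The planned groups are 7 smokers and 7 never smokers (Protocol 12.2, SAP 5.1), and the AE tables are by group. One participant whose only AE is misfiled changes his group's percentage by 1/7 = 14.3 points.

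The documents give no rate for Visit 1 reactions. Take p as an assumed chance of a clinically relevant reaction per enrolled participant, independent between participants. The chance of at least one among 14 is 1 − (1 − p)^14:

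- p = 1%: 1 − 0.99^14 = 13.1%
- p = 5%: 1 − 0.95^14 = 51.2%
- p = 10%: 1 − 0.90^14 = 77.1%

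These are chances that the classification question arises, not chances that an event is lost. Section 7.2 also requires inclusion criterion 4 (good health) to be rechecked after a clinically relevant Visit 1 finding. Some participants with a reaction may therefore not be enrolled, and would be outside the safety population under either rule.

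**The case against.** The strongest reply is that the AE provisions already settle the matter. The definition in 8.1.1, the collection period in 8.2.2, the AE query at screening, the Visit 1 entry in Appendix A and the capture window in 11.2 all lead to an AE record. Section 7.2.4 keeps a post-consent reaction out of concomitant disease. Only 7.2 points the other way. This stands as far as it goes: many sites would record the AE. But 7.2 is worded as a requirement, and nothing says which section prevails.

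The rule also covers only clinically relevant findings, so minor reactions fall outside its concomitant-disease limb. Appendix A lists vital signs once at Visit 1 and specifies no repeat after the bronchodilator, so a changed pulse might not be measured. Visit 1 vital signs would still appear in Table A 10 and Listing 12, and laboratory values in Tables A 13 to A 15 and Listing 15. What is at risk is classification as an AE, not those measurements. Section 2.3.2 names spirometry only as an example and rates the procedure risks as comparable to those of routine health examinations. All of this stands and limits the size of the point.

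A reader might infer two stronger things.

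- *That all same-visit reactions to spirometry and skin prick testing will be misfiled.* That is the ceiling if every site lets 7.2 override the other sections. Nothing in the documents makes it an expected rate.
- *That 11.2 confines the database to enrolled subjects, so AEs in screen failures are lost.* Section 11.2 says that enrolled subjects are entered in the eCRF; it does not say that only they are. The sentence before it has screening-failure and AE data captured in source documents from consent. SAEs are reportable from consent in any case, and a safety population of enrolled subjects is an explicit choice. How 8.2.1, which asks for AEs on the CRF, relates to 11.2 for screen failures is at most a separate minor clarification.

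**Conclusion.** The contradiction is in the current text. Section 7.2 conflicts with 7.2.4, 8.2.2 and Appendix A on new conditions that arise after consent at Visit 1, and with 8.5.1 on screening laboratory findings. If 7.2 is followed, a new, clinically relevant reaction to a Visit 1 procedure gets no relatedness judgement and is missing from the AE tables.

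The conclusion assumes that the event is clinically relevant, is seen at Visit 1 in someone later enrolled, and is classified by 7.2 rather than by the other sections. The likely number of such events cannot be derived from the documents. The effect is confined to the secondary safety objective; the STT and nicotine analyses do not depend on it. It should be corrected because the safety rules must agree, but it does not threaten the study's primary aims.

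**What to change.** Reword 7.2 to use the boundary already in 7.2.4 and 8.2.2:

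- A condition that began before the consent form was signed and was ongoing at that time is concomitant disease.
- A new or worsened occurrence after signature, including during or after a Visit 1 procedure, is an AE.
- For laboratory abnormalities in the screening sample, where onset is usually unknown, refer to the case-by-case assessment in 8.5.1.

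This adopts the protocol's own definition and changes no procedure, visit, population or planned table. The cost is a short wording amendment to 7.2. The one downside is that a few screening-day AEs may be added to Tables A 11 and A 12.
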